Justification: These adjustments have been made to provide greater flexibility to sites and subjects in scheduling these visits. In exceptional circumstances, sites will now have the ability to perform selected assessments at a subject’s home or by telephone, with prior

approval of the Sponsor. This modification has been made to help mitigate the risk of critical primary endpoint related data not being collected due to challenges associated with conducting the study with an elderly population in which subjects approaching endpoint are repeatedly triggering which requires additional visits, increasing subject burden and study fatigue.

5. Microscopic urine screens will be standard on all urine sample collections at routine visits rather than as a reflex in the event of abnormalities detected on macroscopic examination.

Justification: This change has been made to eliminate the need for additional site visits, which will decrease subject burden.

6. Formal limits for assessment of compliance with study drug have been introduced.

Justification: Limits have been introduced to the protocol to help facilitate consistency in global monitoring and reporting of subjects that are not compliant with administration of study drug.

7. Clarification provided over Adverse Event of Special Interest (AESI) follow-up and reporting of macular degeneration and hypoglycemia.

Justification: Clarification provided to ensure consistency in follow-up of macular edema and to eliminate ambiguity over reporting of hypoglycemia as an AESI, ensuring consistency across all subjects.

TABLE OF CONTENTS

1.0 ADMINISTRATIVE INFORMATION 3

 1.1 Contacts..... 3

 1.2 Approval..... 4

 1.3 Protocol Amendment 6 Summary of Changes 6

2.0 STUDY SUMMARY 14

3.0 STUDY REFERENCE INFORMATION 18

 3.1 Study-Related Responsibilities..... 18

 3.2 Principal Investigator/Coordinating Investigator 18

 3.3 List of Abbreviations 19

 3.4 Corporate Identification 22

4.0 INTRODUCTION..... 23

 4.1 Background 23

 4.2 Rationale for the Proposed Study 25

 4.2.1 Genetic Risk Factors for AD 26

 4.2.2 Pioglitazone 29

 4.2.3 Mild Cognitive Impairment due to Alzheimer’s Disease (MCI due to AD)..... 30

5.0 STUDY OBJECTIVES AND ENDPOINTS..... 33

 5.1 Objectives..... 33

 5.1.1 Primary Objectives..... 33

 5.1.2 Key Secondary Objectives 33

 5.1.3 Additional Objectives..... 33

 5.2 Endpoints..... 34

 5.2.1 Primary Endpoints 34

 5.2.2 Key Secondary Endpoints 34

 5.2.3 Additional Endpoints 34

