9.1.8 Procedures for Clinical Laboratory Samples

All samples will be collected in accordance with acceptable laboratory procedures. The maximum volume of blood at any single visit is approximately 16 mL, and the approximate total volume of blood for the study is 87 mL. Details of these procedures and required safety monitoring will be given in the laboratory manual. [Table 9.a](#) lists the laboratory tests that will be required by the protocol. Laboratory samples will be taken at the time points stipulated in the Schedule of Study Procedures ([Appendix A](#)).

Table 9.a Clinical Laboratory Tests

Hematology	Serum Chemistry	Urinalysis
Red blood cells	Alanine aminotransferase	pH
White blood cells count with differentials (Neutrophils, Eosinophils, Basophils, Lymphocytes, Monocytes)	Alkaline phosphatase Aspartate aminotransferase Total bilirubin Direct bilirubin (a) γ -Glutamyl transferase	Specific gravity Protein Glucose Blood Nitrite
Hemoglobin	Total protein	Microscopic examination (Leucocytes, Erythrocytes, Casts)
Hematocrit	Albumin	
Platelets	Creatinine	
HbA1c (b)	Blood urea nitrogen Potassium Sodium Glucose Calcium, parathyroid hormone (PTH) Thyroid-stimulating hormone (TSH), free thyroxine (T4) Vitamin B12, folate (c) Rapid plasma reagin (RPR) (c)	

Blood

Hepatitis panel, including HBsAg and anti-HCV (b)

(a) Assess only if total bilirubin ≥ 2.0 mg/dL.

(b) To be done at Baseline only.

(c) At Baseline and as part of the comprehensive medical follow-up evaluation to rule out other causes of dementia.

The central laboratory will perform laboratory tests for hematology, serum chemistries, and urinalysis. The results of laboratory tests will be returned to the investigator, who is responsible for reviewing and filing these results.

A separate contract laboratory will perform the TOMM40 rs10524523 and APOE genotyping. The result of the genotyping will remain blinded to the site, subject, and study team.

Should the subject be excluded from the study due to acute lab exclusions (eg, blood in urine) at Visit 2 that may resolve upon retesting, the subject is permitted to be retested within a window of 2 weeks. Re-testing will only be allowed on safety lab data, not cognitive testing or at Visit 1 for the risk stratification sample. In this situation, sites should not enter that the subject baseline failed into the electronic data capture (EDC) or IVRS until the retest results are completed and verified.

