4. Bone fractures: All female subjects, regardless of their clinical risk factors for osteoporosis, should be encouraged to eat a balanced diet and participate in appropriate exercise, avoid cigarette smoke and excessive alcohol consumption. All postmenopausal women should be encouraged to employ lifestyle practices that reduce the risk of bone loss and osteoporotic fractures: maintaining a healthy weight, eating a balanced diet, obtaining adequate calcium and vitamin D, participating in appropriate exercise, avoiding excessive alcohol consumption, not smoking. An adequate intake of both calcium and vitamin D is important for bone health and is recognized as an important component of any osteoporosis prevention drug regimen [68]. Among women age 75 and older, muscle strengthening and balance exercises have been shown to reduce the risk of falls and fall-related injuries by 75% [69]. Weight-bearing exercise can be as simple as brisk walking. All suspected or confirmed bone fracture will be followed-up for an X-ray confirmation, outcome, and any healing complications. Current standards of care for assessing and maintaining bone health will be applied.
5. Bladder cancer: Subjects and their project partners will be advised to promptly report any signs or symptoms that could be consistent with bladder cancer such as hematuria, urinary urgency, urinary frequency, or dysuria. Any subject with previous or active bladder cancer

will be excluded. All subjects will be screened for evidence of hematuria (macroscopic or microscopic). In the event of unexplained hematuria (3 or more red blood cells per high power field on microscopic urine test), confirmed by a repeat test (within 14 days of the initial assessment), subject will be referred to a urologist for additional follow-up testing according to local standard diagnostic approach. If the diagnosis of the bladder cancer cannot be excluded the subject will be withdrawn from the study.

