5.0 INTRODUCTION

This document describes the statistical analyses to be performed and data presentations to be produced for this phase 3, randomized, double-blind, parallel-group, placebo-controlled study to simultaneously qualify a biomarker algorithm for prognosis of risk of developing mild cognitive impairment due to Alzheimer's Disease (MCI due to AD) and to test the safety and efficacy of pioglitazone (AD-4833 SR 0.8 mg QD) to delay the onset of MCI due to AD in cognitively normal subjects.

The purpose of this statistical analysis plan (SAP) is to ensure the credibility of the study findings by specifying the statistical approaches to the analysis of the double-blind data prior to database lock. This SAP was developed based on the International Conference on Harmonisation (ICH) E3 and E9 Guidelines and in reference to the following documents:

- Protocol AD-4833/TOMM40_301 Amendment #1 dated 09 April 2013.
- Protocol AD-4833/TOMM40_301 Amendment #2 dated 19 March 2014.
- Protocol AD-4833/TOMM40_301 Amendment #3 dated 10 November 2014.
- Protocol AD-4833/TOMM40_301 Amendment #4 (Local-Russia) dated 15 April 2015.
- Protocol AD-4833/TOMM40_301 Amendment #5 dated 24 July 2015.

Any deviations during the analysis and reporting process from the current statistical analysis plan will be described and justified in the final report. Analysis issues that suggest changes to the principal features stated in the protocol will be documented in a protocol amendment. Otherwise, the statistical analysis plan will be updated through an amendment with the changes in the analyses documented in the amendment.

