9.14.2 Clinical Laboratory Evaluations

The following clinical laboratory parameters will be summarized:

- Serum chemistry including alanine aminotransferase (ALT), alkaline phosphatase, aspartate aminotransferase (AST), total bilirubin, GGT, total protein, albumin, creatinine, blood urea nitrogen (BUN), potassium, sodium, glucose, calcium, vitamin B12, folate, parathyroid hormone (PTH), thyroid stimulating hormone (TSH), and free thyroxine (free T4). (Direct bilirubin will be assessed only if total bilirubin ≥ 2.0 mg/dL. Vitamin B12, folate, and RPR is

collected only at Baseline and as part of the comprehensive medical follow-up evaluation to rule out other causes of dementia).

- Hematology including red blood cells, white blood cells, neutrophils, eosinophils, basophils, lymphocytes, monocytes, hemoglobin, hematocrit, platelets, and HbA1c. (HbA1c is collected only at Baseline.)
- Urinalysis including pH, specific gravity, glucose, and nitrite. (Protein and blood values will not be summarized but will be included in the listings.)

For each laboratory parameter, the following will be displayed for each scheduled time point (each visit and end of study).

- Summary statistics (n, mean, SD, median, minimum, and maximum) by treatment group and overall for the actual values and change-from-Baseline values.
- Shift tables for the change from Baseline to each post-baseline time point will be presented. For these tables each subject will be categorized as low, normal, or high for the baseline value and low, normal, or high for each post-Baseline time point, according to the central laboratory reference ranges. The number of subjects in each of the combinations of shifts will be presented.
- Markedly abnormal values for laboratory parameters, as defined in [Appendix A](#), will be summarized by treatment group and overall. The number and percentage of subjects with MAV values observed post-Baseline in each of the applicable laboratory parameters will be presented.
- Number and percentage of subjects with elevated liver enzyme lab values will be presented using the criteria described in the protocol.

Subject mappings will be provided for markedly abnormal lab values and elevated liver enzyme lab values.

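### Laboratory-detected hematuria, the protocol's in-study bladder cancer screen, has no by-treatment laboratory summary in the SAP and reaches a by-arm table only if the investigator records it as an adverse event

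*SAP*

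**What the plan says.** Protocol 10.2.1.3, item 5 (bladder cancer), states that "All subjects will be screened for evidence of hematuria". The action criterion is "unexplained hematuria (3 or more red blood cells per high power field on microscopic urine test), confirmed by a repeat test", with the repeat due within 14 days. A confirmed finding leads to urology referral.

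Protocol Table 9.a (section 9.1.8) lists urine blood and urine microscopy, including erythrocytes, as separate urinalysis items. The Amendment 6 summary (Protocol 1.3) adds that "Microscopic urine screens will be standard on all urine sample collections at routine visits". Protocol Appendix A schedules urinalysis at baseline, yearly, at comprehensive medical follow-up visits and at end of study or early withdrawal.

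Protocol 13.1.6 says that observed laboratory values and changes will be summarized for each treatment group, and that out-of-range and potentially clinically significant values will be flagged and tabulated.

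SAP 9.14.2 limits the summarized urine parameters to "Urinalysis including pH, specific gravity, glucose, and nitrite" and adds that "Protein and blood values will not be summarized but will be included in the listings". Microscopic erythrocytes are not mentioned. The urinalysis table in SAP Appendix A reads N/A for every parameter, blood included. SAP 9.17, which lists changes from the protocol's analysis plan, mentions only academic degrees.

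**The concern.** The protocol names bladder cancer as an adverse event of special interest and sets up an objective laboratory screen for it. The SAP then keeps the results of that screen out of every laboratory table. The dipstick result is excluded by an explicit rule. The microscopic red-cell count, which carries the protocol's threshold, is left out by silence.

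If the SAP is followed as written, a reader of the study report can see how many subjects in each arm crossed the protocol's liver-enzyme thresholds. The reader cannot see how many crossed its red-cell threshold, unless the finding was also written up as an adverse event or someone counts it by hand from the listings. At stake is whether a screening result for a named risk, in cognitively normal volunteers, is shown by arm from measured values or only through investigator reporting.

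**Working it through.** **1. Does any laboratory display in the SAP capture hematuria by arm?** SAP 9.14.2 provides four displays.

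| Display in SAP 9.14.2 | Urine blood (dipstick) | Microscopic erythrocytes |
|---|---|---|
| Summary statistics by group | Excluded by name | Not a listed parameter |
| Shift tables | Excluded by name | Not a listed parameter |
| Markedly abnormal counts | Appendix A: N/A | No row in Appendix A |
| Count against protocol criteria | None | None (exists for liver enzymes only) |

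No laboratory table by arm is specified. Line listings remain, with out-of-range values flagged.

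**2. Is there another route?** Yes. SAP 9.14.1 tabulates treatment-emergent adverse events by system organ class and preferred term, and again by gender and by age group. SAP 9.1.2 requires all three treatment groups in every tabulation. Hematuria recorded as an adverse event is therefore shown by arm.

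**3. Is that route complete?** Three passages say it need not be.
- Protocol 10.1.3 makes a laboratory change an adverse event only when it is judged clinically significant. A re-test, monitoring or added noninvasive testing does not count as an intervention.
- Protocol 10.2.1.3, item 3 (hepatic effects), tells the investigator to record a confirmed, otherwise unexplained enzyme elevation on an adverse event page. Item 5 (bladder cancer) gives no such instruction for confirmed hematuria.
- SAP 9.14.1 has a Bladder Cancer category of special interest but does not say whether hematuria terms fall in it.

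**4. Does the SAP agree with the protocol?** Protocol 13.1.6 exempts no laboratory test from by-group summary or from tabulation of abnormal values. SAP 9.14.2 exempts protein and blood, and SAP 9.17 does not declare this.

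**5. Can the loss be sized?** Not for hematuria, since no rate is given. For context on bladder cancer itself, the inputs are 1,470 subjects per high-risk arm (Protocol 6.1) and 12% annual dropout (Protocol 13.3). As a check on that dropout figure, 1 − 0.88^5 = 47.2%, against the stated 47%.
- Person-years per arm = 1,470 × (1 − 0.88^T)/(−ln 0.88). For T = 4: 1,470 × 3.131 = 4,603. For T = 5: 1,470 × 3.694 = 5,431.
- Assumed incidence of 50 to 200 per 100,000 person-years (not in the documents): 4,603 × 0.0005 = 2.3 cases, up to 5,431 × 0.002 = 10.9 cases, in the placebo arm.
- Power to detect a doubling, two-sided 5%, from the normal approximation for two proportions, Φ[(|p1 − p2| − 1.96·SE0)/SE1], with SE0 pooled and SE1 unpooled: 14% to 48%.

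The same formula for hematuria, with assumed placebo proportions and 1,470 per arm:

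| Placebo proportion (assumed) | Ratio 1.5 | Ratio 2 |
|---|---|---|
| 1% | 23% | 61% |
| 2% | 41% | 89% |
| 5% | 80% | >99% |
| 10% | 98% | >99% |

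The answer runs from poor to very good depending on a figure the documents do not supply, so no power claim can be made for the missing table.

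**The case against.** The best defense is the adverse event route. Under Protocol 10.1.3 a finding that requires action qualifies as an adverse event, and confirmed unexplained hematuria triggers urology referral. That is more than a re-test, so the cases that matter most may well be recorded and then shown by arm. Bladder cancer stays a summarized category of special interest, values are listed, and the monitoring board reviews all safety data periodically (Protocol 11.2). This stands as far as it goes. It does not make capture certain, because item 5 lacks the recording instruction that the liver item has. Listings and board review also do not put a by-arm count in the study report.

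A reader might infer more than the documents support in four ways.
- That hematuria is never compared between arms. It is, whenever it is recorded as a treatment-emergent event.
- That it is the one bladder signal frequent enough to compare. No hematuria rate is given, and item 5 also names urgency, frequency and dysuria.
- That the quoted exclusion removes the threshold variable. It removes the dipstick value. The microscopic count is omitted by silence.
- That the SAP missed routine microscopy because the last protocol version it cites is "Protocol AD-4833/TOMM40_301 Amendment #5 dated 24 July 2015". Its text already contains the operational futility assessment and the 33% futility analysis introduced by Amendment 6, so the stale citation list does not explain the omission.

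Two further cautions bear on the remedy. The superseded footnote reproduced in Protocol Appendix J shows that microscopy was done only after another abnormal urine result until Amendment 6, which was signed in October 2016, so ascertainment is mixed. In addition, the protocol criterion requires the hematuria to be unexplained, a clinical judgement that cannot be derived from laboratory values.

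**Conclusion.** The point holds in a limited form. The SAP specifies no by-treatment laboratory summary for either urine blood or microscopic erythrocytes. Laboratory-detected hematuria reaches a by-arm table only through discretionary adverse event recording. This conflicts with Protocol 13.1.6 and is not declared in SAP 9.17. The protocol's liver-enzyme thresholds, by contrast, do get their own table.

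The affected data are the post-baseline urine results of about 3,500 randomized subjects. The number of findings that would escape the adverse event tables is unknown. The conclusion rests on reading the documents side by side and does not depend on the assumed rates above. It does not mean that the trial loses its bladder safety comparison. It is an SAP alignment point that is worth making because the remedy is cheap.

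**What to change.** In SAP 9.14.2, remove blood from the not-summarized sentence and add urine erythrocytes to the urinalysis parameters. Present, for all three treatment groups, the number and percentage of subjects with:
- any post-baseline result of 3 or more red cells per high power field;
- that result confirmed on repeat.

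State that unscheduled repeat samples count. SAP 9.1.3 otherwise keeps only the result closest to the scheduled day in each visit window, which could drop either the initial or the confirmatory sample.

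Label the table as laboratory hematuria, not as the full protocol criterion. Note the change from reflex to routine microscopy, and either split the results by period or show dipstick blood alongside. Enter the criterion in the urinalysis part of SAP Appendix A. State in SAP 9.14.1 whether hematuria terms belong to the Bladder Cancer category. Bring 9.14.2 into line with Protocol 13.1.6, or declare the remaining difference (urine protein) in 9.17.

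The table is descriptive and needs no test. The cost is one or two extra tables from data already held, with no new procedure for subjects. The downside is mixed ascertainment before and after Amendment 6, which the labelling should make plain.

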9.14.3 Vital Signs

Vital signs and weight at scheduled visits and their changes from Baseline will be summarized for each treatment group and overall using descriptive statistics by visit and end of study. The number and percentage of subjects with at least one post-Baseline MAV vital sign value during the double-blind treatment period will be presented for each variable over all visits. A listing of MAV vital signs values will also be presented. The criteria for identification of MAV vital signs values are provided in [Appendix B](#).

9.14.4 Physical Examinations

All physical examination findings will be listed by treatment, study center and subject number. The following variables will be listed: subject identifier, age, gender, study visit, visit date, body system, whether there was an abnormality, and, a description of the abnormality.

9.14.5 12-Lead ECGs

ECG variables at scheduled visits and their changes from Baseline will be summarized for each treatment group and overall using descriptive statistics by study visit and end of study. A shift table for the investigator's ECG interpretation will provide the number of subjects in each of the appropriate categories (Normal, Abnormal but not clinically significant, or Abnormal and clinically significant) at the scheduled visit relative to the Baseline status. The number and percentage of subjects with at least one post-Baseline MAV ECG value during the double-blind treatment period will be presented for each variable over all visits. A listing of MAV ECG values will also be presented.

The criteria for identification of MAV ECG values are provided in [Appendix C](#).

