Few postmarketing reports of new-onset or worsening diabetic macular edema with decreased visual acuity have occurred with TZDs, including pioglitazone. Many of these patients reported concurrent peripheral edema. It is not known whether there is a direct association between pioglitazone and macular edema, but investigators should be alert to the possibility of macular edema. If study participants report disturbances in visual acuity (eg, blurred vision, distortion of images, missing areas, dimming or “graying-out” of vision from loss of contrast sensitivity, and changes in the way color is perceived), they will be evaluated by an ophthalmologist.

There have been postmarketing reports of bone fractures associated with the use of TZDs, including pioglitazone. The majority of the fractures occurred in women with most of the fractures involving upper and lower limbs of the body. Many cases lack any information about history or about risk factors for bone fractures. In cases where information was available, patients had a history of and multiple risk factors for fractures.

Adverse events associated with pioglitazone, listed in the Warnings and Precautions section of the Company Core Data Sheet [20], for subjects with T2DM and at doses considerably higher (15-45 mg) than the intended dose in this clinical development program (sustained release [SR] 0.8 mg) were as follows: congestive heart failure (CHF) and peripheral edema due to dose-related fluid retention, hepatic failure, increased incidence of fractures in female population, hypoglycemia, macular edema, and bladder cancer. A detailed discussion of the safety profile of pioglitazone is provided in the investigator’s brochure.

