6.3.2 Study Dose

Because studies for AD prevention require long treatment durations and large study populations, it is not practical to do typical phase 2 studies prior to initiating phase 3 studies. As such a phase 2 program (including dose finding) was not conducted prior to the AD-4833/TOMM40_301 study. Still, there are a number of preclinical studies that indicate that pioglitazone increases mitochondrial numbers, motility and function at very low doses (relative to doses used to treat T2DM) [7]. This effect on mitochondria is hypothesized to be the key mechanism of action (MOA) for pioglitazone's ability to delay the onset of MCI due to AD. In addition to these preclinical studies, an imaging study (using functional magnetic resonance imaging [fMRI] was carried out in cognitively normal elderly subjects). From this study, it was ascertained that pioglitazone has central nervous system (CNS) effects at low doses and that there is a demonstrable blood oxygen level-dependent (BOLD) effect in the left hippocampus during an encoding task for episodic memory. This was a significant factor in dose selection because the intended AD-4833/TOMM40_301 study population is cognitively normal elderly adults, and the overall goal in dose selection was to minimize known dose-dependent adverse events (eg, edema) while ensuring that pioglitazone can still directly influence brain activity. Based on the available literature and the results of the fMRI study, pioglitazone sustained release (SR) 0.8 mg was selected for phase 3.

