9.1.3 Physical Examination Procedure

A baseline physical and neurological examination (defined as the pretreatment assessment at Baseline (Visit 2) will consist of the following body systems: (1) eyes; (2) ears, nose, throat; (3) cardiovascular system; (4) respiratory system; (5) gastrointestinal system; (6) dermatologic system; (7) extremities; (8) musculoskeletal system; (9) nervous system; (10) lymph nodes; and (11) other. All subsequent physical and neurological examinations should assess clinically significant changes from the baseline examination. Physical examination will be performed at Visit 2 (Baseline), each yearly visit (eg, month 12, 24, 36) of double-blind treatment, Unscheduled Visit, and EoS/EW Visit. Neurological examination will be performed at Visit 2 (Baseline), every 6 month visit during double-blind treatment, Unscheduled Visit, and EoS/EW Visit.

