10.2.1.3 AESI Reporting

The phase 3 efficacy and safety study will be conducted in cognitively normal elderly subjects. Pioglitazone appears to be safe and well tolerated in the elderly population, based on the available information from healthy volunteers and diabetics in Takeda-sponsored trials or from AD patients in Takeda-supported studies [15,16]. Based on the available safety information in the diabetic population, the following safety procedures will be implemented when specific AESIs are reported during the study. All such AEs will be reported to the Sponsor in an expedited manner irrespective of the event's seriousness or causal relationship:

1. Congestive heart failure (CHF): Subjects and their project partners will be advised to promptly report signs and symptoms of heart failure (eg, excessive, rapid weight gain, dyspnea, and/or edema). Any subject with CHF NYHA class III-IV will be excluded at screening. If a subject develops a new onset CHF or experiences deterioration of pre-existing condition after enrollment, the subject will be withdrawn from the study. Assessment of subjects for signs and symptoms of CHF will take place at every study visit. The diagnosis of CHF can be difficult. Many of the symptoms of heart failure are nondiscriminating and, therefore, of limited diagnostic value. Many of the signs of heart failure result from sodium and water retention and resolve quickly with diuretic therapy, ie, may be absent in patients receiving such treatment. Because the signs and symptoms of heart failure are so non-specific, demonstration of an underlying cardiac cause using diagnostic tests (such as ECG, echocardiogram, chest X-ray, etc) is very important to the diagnosis of heart failure. For

CONFIDENTIAL

events of heart failure, a CHF eCRF should be completed within 24 hours of the investigator's awareness of the event.

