13.1.6 Safety Analysis

AEs

AEs will be reported throughout the study.

CONFIDENTIAL

Treatment-emergent AEs are any new or worsened events that occurred after the first dose of study medication and within 30 days following discontinuation of study medication. AEs will be coded using MedDRA and will be summarized by system organ class and preferred term.

AEs that were reported more than once by a subject during the same period will be counted only once for that subject and period at the maximum severity.

Clinical Evaluations

Observed values and changes from screening/baseline in clinical safety laboratory tests, vital signs, ECG parameters, and body weight will be summarized for each treatment group using descriptive techniques. Values outside normal ranges and potentially clinically significant values will be flagged and tabulated. Physical examination findings will also be summarized for each treatment group.

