7.2.1 Additional Endpoints

7.2.1.1 Safety Assessments

- Safety and tolerability: adverse events (including adverse events of special interest), vital signs, body weight, electrocardiogram (ECG), clinical laboratory data, and physical exam findings.

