9.17 Changes in the Statistical Analysis Plan from the Protocol Analysis Plan

The study protocol states that academic degrees at baseline will be listed and summarized by treatment group and overall. Information about academic degrees is not collected directly in the eCRF and so won't be presented in the CSR.

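### The SAP only lists physical examination findings, although the protocol requires a summary by treatment group, and the change is not declared

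*SAP*

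**What the plan says.** Protocol 13.1.6 (Safety Analysis), after providing for laboratory, vital sign, ECG and weight summaries, adds: "Physical examination findings will also be summarized for each treatment group". SAP 9.14.4 provides instead: "All physical examination findings will be listed by treatment, study center and subject number". The listing variables include study visit, body system, whether an abnormality was present, and its description. No count, percentage or shift table is planned.

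Both documents treat these findings as a safety assessment in their own right. The list in SAP 7.2.1.1 ends with "clinical laboratory data, and physical exam findings", and Protocol 5.2.3.1 gives the same items. SAP 9.17 reports a single departure from the protocol: "The study protocol states that academic degrees at baseline will be listed and summarized by treatment group and overall", followed by the reason this cannot be done.

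Protocol 9.1.3 sets out the examination by body system, including eyes, cardiovascular, respiratory and extremities, at baseline, yearly, at unscheduled visits and at end of study or early withdrawal (EoS/EW). It adds: "All subsequent physical and neurological examinations should assess clinically significant changes from the baseline examination".

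**The concern.** A summary that the protocol promises for a named safety assessment has become a subject-level listing, and the section meant for such changes is silent. The study estimates about 3,500 randomized subjects, so a listing, even one sorted by treatment, does not give the reader numbers by arm.

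The examination is relevant to this drug. Protocol 4.1 names "congestive heart failure (CHF) and peripheral edema due to dose-related fluid retention" among the warnings for pioglitazone, although at doses of 15 to 45 mg, well above the SR 0.8 mg studied here. Protocol 6.3.2 gives the avoidance of dose-dependent events, with edema as the example, as a goal of dose selection. Subjects are cognitively normal, and Protocol 4.2.2 sets a high safety threshold for them. By-arm counts of examination findings would be part of the evidence on whether that goal was met.

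**Working it through.** No sample size, power or error rate enters this point, so there is nothing to recompute. The check compares the texts.

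1. **Is there a conflict?** Protocol 13.1.6 requires a summary by treatment group, and SAP 9.14.4 plans a listing. The opening of SAP 9.14 says in general terms that safety summaries will be descriptive and by treatment group, but it specifies no physical examination table.

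2. **Does document version explain it?** SAP 5.0 cites the protocol only up to Amendment 5, while the protocol supplied is Amendment 6. Protocol Appendix J, which details the Amendment 6 changes, shows none to 13.1.6. Version lag is therefore not the explanation.

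3. **Is it a stated choice?** Where the SAP drops a summary on purpose, it says so. SAP 9.14.2 states that urine protein and blood, direct bilirubin and RPR are listed and not summarized. SAP 9.14.4 has no such statement, and SAP 9.17 does not mention the change. Laboratory data, vital signs and ECG (SAP 9.14.2, 9.14.3, 9.14.5) all receive by-arm summaries.

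4. **Was a by-visit table expected?** SAP Table 9.a assigns physical examination (PE) to a column of analysis windows (for example, days 2 to 547 for Month 12). SAP 9.1.3 says that windows are not applied to listings of eCRF data. If findings are only listed, those windows have no use. This is supportive but not conclusive, because DNA/RNA sampling shares the column.

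5. **What reaches a by-arm table by another route?**
   - Heart failure, as a special-interest category (SAP 9.14.1).
   - All treatment-emergent adverse events by system organ class and preferred term, including any edema terms (SAP 9.14.1).
   - Weight by visit, and a flag for change above 7% (SAP 9.14.3 and Appendix B).

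6. **What does not?** Examination abnormalities that were not recorded as adverse events. Two features of the protocol make this group plausible. Protocol 10.1.3 directs that signs accompanying a recorded diagnosis are not entered as separate events. Also, peripheral edema is in the Protocol 4.1 warnings but is not one of the six special-interest categories in SAP 9.14.1, so it is counted only if reported as an adverse event.

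**The case against.** The strongest reply is that the harms of interest are already covered. Protocol 10.2.1.3 gives edema as an example of a heart failure sign and states: "Assessment of subjects for signs and symptoms of CHF will take place at every study visit". That is more often than the yearly examination. Investigators assess adverse events at each study visit (Protocol 10.2.1.2), and an unfavorable sign can itself be an adverse event (Protocol 10.1.2). The DSMB reviews all safety data (Protocol 11.2), and the listing is sorted by treatment. All of this stands, and it limits the consequence.

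It also rules out several stronger readings. A reader might infer that the physical examination is the only scheduled, solicited check for edema, or that the evidence on edema rests only on spontaneous reports. The visit-by-visit heart failure assessment and adverse event assessment contradict both. A reader might infer that edema and heart failure are never compared between arms, or that nobody looks at the examination data by arm. The adverse event, special-interest and weight tables contradict the first, and the DSMB's remit means the documents do not support the second. The protocol also describes a general examination by body system, not one aimed at edema.

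A reader might take the edema rate in the 18-month pilot cited in Protocol 4.1, 28.6% against 0%, as the size of the problem. That is 4 of 14 subjects (4/14 = 28.6%) titrated to 45 mg/day. It says little about SR 0.8 mg.

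Finally, the protocol says only that findings will be summarized. It does not prescribe a shift table, so the layout proposed below is a suggestion for meeting the requirement.

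**Conclusion.** The point holds as an undeclared departure from a protocol-required safety summary. The loss is confined to by-arm counts of examination abnormalities that never became adverse event records, such as mild peripheral edema. The documents do not allow that number to be estimated at the study dose, and no primary or key secondary result depends on it. SAP safety output is descriptive, so the missing item is a side-by-side tabulation, not a test.

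The conclusion assumes that some examination abnormalities are not reported as adverse events, as Protocol 10.1.3 permits. It also assumes that no separate table specification, not supplied here, already contains the summary.

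**What to change.** In SAP 9.14.4, add a table by treatment group with the number and percentage of subjects who have a new abnormality since baseline, by body system and scheduled visit, using the PE windows in Table 9.a. Keep the listing. Three details should be stated:

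- **What counts as new.** Later examinations are meant to record clinically significant changes from baseline, so the SAP should say whether a post-baseline flag already means a change or must be compared with the baseline flag for that body system.
- **Which examinations count.** Comprehensive medical follow-up visits (CMFVs) are triggered by cognitive outcomes, so their frequency could differ by arm if treatment affects cognition. If a row for any post-baseline time is added, restrict it to scheduled and EoS/EW examinations, or show CMFV examinations separately. The windows select the result closest to the target day, so a CMFV examination could also fill a window when the yearly one is missing. The SAP should say whether that is allowed.
- **Denominator.** Use subjects examined for that body system at baseline and in the window.

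The cost is one descriptive table from variables already in the listing, with no new data collection and no effect on type I error. If the sponsor prefers the listing alone, the change from Protocol 13.1.6 should be declared and justified in SAP 9.17. That would remove the inconsistency but would not supply the counts.
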